A per protocol analysis of the primary endpoint will include endpoints that occur in patients who complete the study fully compliant with the protocol and without any major violation or deviation (defined in the SAP).

For the secondary efficacy outcomes, analyses will be performed using the primary efficacy data set.

The apixaban-to-comparator Hazard Ratio adjusted for the competing risk of death unrelated to VTE will be computed with associated two-sided 95% Confidence Interval by resorting to the Fine & Gray regression model (Fine and Gray, 1999) using treatment group and center as dummy covariates.

Apixaban will be considered non-inferior to the comparator dalteparin if the upper two-sided 95% confidence limit of hazard ratio is < 2.00. Superiority of apixaban vs. dalteparin will be tested as a secondary analysis of the primary endpoint, only after non-inferiority has been demonstrated for the experimental treatment group (apixaban) relative to the standard treatment group (dalteparin). According to CPMP/EWP/482/99 document entitled: "Points to consider on switching between superiority and non-inferiority", switching the apixaban vs. dalteparin contrast from the non-inferiority objective to the superiority objective is feasible because the trial is properly designed in accordance to the strict requirements of a non-inferiority trial.

Caravaggio Study Protocol FINAL Version 3.0, May 22nd 2018

	For the purpose of safety analyses, subjects will be categorized to the group to which they were assigned at randomization unless incorrect study treatment was received throughout the study, in which case the subject will be categorized according to the treatment received. All safety analyses will be conducted on the safety population. The term "treatment period" refers to the period between the first administration of study drug and 48 hours after the last administration of study drug. This period will be the basis for the summaries of safety.
Study Sites and Location:	Approximately 140 study sites in 11 countries are planned to enroll patients in this study

TABLE OF CONTENTS

SYNOPSIS	2
1. LIST OF ABBREVIATIONS	12

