10.6. Efficacy Analyses

Analysis of Primary Endpoint

Analyses of the primary efficacy endpoint will be performed using the modified intent-to-treat and the intent-to treat principle and the per protocol principle. The modified intent-to-treat and the intent-to-treat analyses of the primary endpoint will include endpoints that occur at any time from randomization until the end of their originally intended treatment period regardless of whether subjects were receiving study medication.

The primary efficacy variable, i.e. the time from randomization to the first recurrent thromboembolic event, will be analyzed after adjusting estimates for the competing risk of death unrelated to VTE (21). The competing risk analysis will be performed using the SAS macro %PSHREG (22) while the probabilities of failure for the event of interest (first recurrent thromboembolic event) are displayed using cumulative incidence plots which do account for the competing risk (death unrelated to VTE).

The null hypothesis to be tested will be that apixaban is inferior to dalteparin in the prevention of recurrent thromboembolic events during 6-month follow-up; i.e. $H_0 \rightarrow E[HR] \ge 2.00$.

The alternative hypothesis will be that apixaban is non-inferior to dalteparin in the prevention of recurrent thromboembolic events during 6-month follow-up; i.e. $H_a \rightarrow E[HR] < 2.00$.

Where: E[HR] is the Expected (E) apixaban-to-comparator Hazard Ratio (HR), while 2.00 is the prefixed non-inferiority threshold.

The evaluation of the primary objective will be done by considering the time from randomization to the first recurrent thromboembolic event (event of interest) or to the occurrence of death unrelated to VTE (nuisance/competing event) or to the last follow-up if neither a recurrent thromboembolic event nor a competing event occurred within the 6-month follow-up (censored time). The apixaban-to-comparator Hazard Ratio adjusted for the competing risk of death unrelated to VTE will be computed with associated two-sided 95% confidence interval by resorting to the Fine & Gray regression model (23) using treatment group and center as dummy covariates. Apixaban will be considered non-inferior to the comparator dalteparin if the upper two-sided 95% confidence limit of Hazard ratio is < 2.00.

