Superiority of apixaban vs. dalteparin will be tested as a secondary analysis of the primary endpoint, only after non-inferiority has been demonstrated for the experimental treatment group (apixaban) relative to the conventional treatment group (dalteparin). According to CPMP/EWP/482/99 document entitled: "Points to consider on switching between superiority and non-inferiority", switching the apixaban vs. dalteparin contrast from the non-inferiority objective to the superiority objective is feasible because the trial is properly designed in accordance to the strict requirements of a non-inferiority trial.

Analysis of Secondary Endpoints

For the secondary efficacy endpoints, analyses will be performed using the primary efficacy data set.

- The individual components of the primary efficacy outcome: The same competing risk model (23) defined above for the analysis of primary efficacy variable will be employed for the analysis of the time from randomization to the first recurrent event among those included in the primary efficacy outcome recurrent (see 4.1). The apixaban-to-comparator Hazard Ratio adjusted for the competing risk of death unrelated to VTE will be computed with associated two-sided 95% confidence interval.
- Symptomatic recurrence of VTE: The same competing risk model (23) defined above for the analysis of primary efficacy variable will be employed for the analysis of the time from randomization to the first symptomatic recurrent thromboembolic event. The apixaban-to-comparator Hazard Ratio adjusted for the competing risk of death unrelated to VTE will be computed with associated two-sided 95% confidence interval.
- Composite of primary efficacy outcome plus major bleeding: The same competing risk model (23) defined above for the analysis of primary efficacy variable will be employed for the analysis of the time from randomization to the composite of primary

efficacy outcome plus major bleeding. The apixaban-to-comparator Hazard Ratio adjusted for the competing risk of death unrelated to VTE or major bleeding will be computed with associated two-sided 95% confidence interval.

- All cause of death: Event free survival will be estimated according to Kaplan-Meier and the event free survival in the two treatment groups will be compared by means of a Cox's proportional hazard model with treatment group and center as dummy covariates. The apixaban-to-comparator Hazard Ratio will be computed with associated two-sided 95% confidence interval.

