- Composite of primary efficacy outcome plus major bleeding plus all cause death: Event free survival will be estimated according to Kaplan-Meier and the event free survival in the two treatment groups will be compared by means of a Cox's proportional hazard model with treatment group and center as dummy covariates. The apixaban-to-comparator Hazard Ratio will be computed with associated two-sided 95% confidence interval.
- Composite of primary efficacy outcome plus all cause death: Event free survival will be estimated according to Kaplan-Meier and the event free survival in the two treatment groups will be compared by means of a Cox's proportional hazard model with treatment group and center as dummy covariates. The apixaban-to-comparator Hazard Ratio will be computed with associated two-sided 95% confidence interval.
- Any fatal or not fatal cardiovascular event: The same competing risk model (23) defined above for the analysis of primary efficacy variable will be employed for the analysis of the time from randomization to the occurrence of any fatal or not fatal cardiovascular event. The apixaban-to-comparator Hazard Ratio adjusted for the competing risk of death unrelated to cardiovascular event will be computed with associated two-sided 95% confidence interval.
- All venous thromboembolic events (including splanchnic vein thrombosis and cerebral vein thrombosis): The same competing risk model (23) defined above for the analysis of primary efficacy variable will be employed for the analysis of the time from randomization to thromboembolic events at sites other than DVT and PE. The apixaban-to-comparator Hazard Ratio adjusted for the competing risk of death unrelated to venous thromboembolic events will be computed with associated two-sided 95% confidence interval.
- Quality of life evaluation (ACTS Scale) (see Appendix 2): For the total score and for each of the subscales, a linear effects model will be estimated with treatment group and center as dummy fixed effects. Results will be reported as Least-Square Means together with associated two-tailed 95% CI and p-value. ITT Analyses will be performed with missing data imputed using conventional LOCF.

Multiplicity

No adjustment for multiplicity is required for the primary efficacy analysis because it is focused on a single time point (6-month) at which only two treatments are being compared.

Center-to-center variability

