Study center and treatment-by-center interactions are included in each of the analyses described above. To assess center-to-center variability, forest plots will be generated to display the results at each center.

Due to the possibility of small numbers of patients at some study sites, some sites may be combined in order to bring the numbers of patients in each pooled site to at least 12. Upon completion of the study and prior to unblinding, study statisticians in consultation with the Steering Committee will determine the pooling based on enrolment numbers and geographical proximity.

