11. FEASIBILITY

Overall, about 140 study centers in Europe and USA, will participate in the study. Each study center is expected to recruit not less than 10 patients in the 18-month recruitment period. The overall study duration (first patient in/last patient out) is estimated to be 25 months.

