to VTE (nuisance/competing event) or to the last follow-up if neither a recurrent thromboembolic event nor a competing event occurred within the 6-month follow-up (censored time). The apixaban-to-comparator Hazard Ratio adjusted for the competing risk of death unrelated to VTE will be computed with associated two-sided 95% confidence interval by resorting to the Fine & Gray regression model using treatment group, center, symptomatic vs unsuspected VTE and active cancer vs history of cancer as dummy covariates. Apixaban will be considered non-inferior to the comparator dalteparin if the upper two-sided 95% confidence limit of Hazard ratio is < 2.00.

Number and percentage of events of interest, competing events and censored patients will be presented as summary of failure outcome. Degrees of freedom (DF), Wald Chi-square and the associated p-value derived from the PHREG model will be also presented.

Superiority of apixaban vs. dalteparin will be tested as a secondary analysis of the primary endpoint, only after non-inferiority has been demonstrated for the experimental treatment group (apixaban) relative to the conventional treatment group (dalteparin). According to CPMP/EWP/482/99 document entitled: "*Points to consider on switching between superiority and non-inferiority*", switching the apixaban vs. dalteparin contrast from the non-inferiority objective to the superiority objective is feasible because the trial is properly designed in accordance to the strict requirements of a non-inferiority trial.

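### Centre dummies in the primary Fine & Gray model cost a few points of power that the sample size does not allow for, and the protocol and SAP disagree on treatment-by-centre interactions

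*SAP*

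**What the plan says.** SAP 10.8.1 specifies a "Fine & Gray regression model using treatment group, center, symptomatic vs unsuspected VTE and active cancer vs history of cancer as dummy covariates". Protocol 10.6 has a "Fine & Gray regression model (23) using treatment group and center as dummy covariates", as does the synopsis, without the two randomisation factors. The upper 95% limit from this model is the figure compared with 2.00.

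On sites, the protocol synopsis says "Approximately 140 study sites in 11 countries are planned to enroll patients in this study". Protocol 11 adds "Each study center is expected to recruit not less than 10 patients in the 18-month recruitment period". Protocol 10.6 (center-to-center variability) and SAP 9.9 permit, but do not require, small sites to be merged until each group has at least 12 patients. The grouping is decided after the study is complete and before unblinding, from enrolment and geography. Randomisation (protocol 6.2, SAP 6.5) is central and stratified by VTE presentation and cancer status, not by centre.

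The sample size (protocol 10.1, SAP 9.3) uses a 7% event rate, a margin of 2.00, 80% power and one-sided alpha 0.025. It gives 934 completers, raised to 1,168 for a loss of up to 20% of patient-years. No other allowance is made.

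On interactions, protocol 10.6 states: "Study center and treatment-by-center interactions are included in each of the analyses described above". SAP 9.9 keeps centre but leaves the interaction out, and the model written out in SAP 10.8.1 has none.

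**The concern.** With 1,168 patients over about 140 sites the mean is 8.3 per site, so even after pooling there may be about as many centre terms as events, or more. A unit with no event has no finite coefficient, and its patients contribute nothing to the treatment comparison; neither document says how such units are handled. Because allocation is not balanced within centre, adjusting for many small centres also uses up treatment information. A truly equivalent drug would then miss the margin more often than the stated 20% of the time.

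The interaction sentence is a separate matter. With a treatment-by-centre interaction in the primary model there would be one treatment effect per centre, and no single hazard ratio to compare with 2.00.

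**Working it through.** **1. The plan's own figure.** Inputs from SAP 9.3: margin 2.00, z = 1.96 and 0.8416, rate 7%, true HR taken as 1 (SAP 9.4 expects a rate no higher than with LMWH).
- Events (Schoenfeld) = 4 × (1.96 + 0.8416)² / (ln 2)² = 65.35.
- 65.35 / 0.07 = 933.5, so 934. 934 / 0.8 = 1,167.5, so 1,168.

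Both stated figures are reproduced by a two-group formula with no covariate term. Expected events are 1,168 × 0.07 = 81.8 with no loss and 81.8 × 0.8 = 65.4 at full loss. Formula power is 88.0% and 80.0% respectively.

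**2. Number of units.** If pooling is carried out, the ceiling is 1,168 / 12 = 97. The documents give no site sizes. Pooling 140 sites of random size to at least 12 gave on average 65 to 76 units, depending on how uneven the sites are, so about 65 is an assumption.

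**3. Units without an event** (Poisson, 65.4 events): exp(−65.4/65) = 37% of 65 units; exp(−65.4/97) = 51% of 97 units.

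**4. Closed-form check.** Treatment information shrinks by about (1 − 1/n), with n patients per unit.
- 65 units, n ≈ 18: 65.35 × 0.944 = 61.7 events, power 77.7%.
- 97 units, n = 12: 65.35 × 0.917 = 59.9 events, power 76.5%.

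The cost is 2.3 to 3.5 points before any small-sample effect of many nuisance terms.

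**5. Simulation at full loss.** True HR 1, 1,168 patients, model-based SE. In runs A and B, loss is 40% of patients leaving uniformly over 6 months and zero-event units drop out of the likelihood.

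| Run | No centre | 65 units | 97 units | Cost in points (65; 97) |
|---|---|---|---|---|
| A: uneven sites pooled within country for 65, equal units for 97; randomisation factors in every model; 6,000 runs | 78.2% | 75.1% | 72.1% | 3.1; 6.1 |
| B: equal units; 3,000-6,000 runs | 79.3% (65), 78.1% (97) | 75.9% | 73.3% | 3.4; 4.8 |
| C: equal units; randomisation factors omitted; 20,000 runs | 78.7% | 75.3% | 73.6% | 3.4; 5.1 |
| D: a further run | 77.5% | 75.3% | 71.9% | 2.2; 5.6 |

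Monte Carlo error in A is 0.4-0.6 points on power and 0.3-0.4 on the paired cost. Simulated power without centre is already 1-2 points below the formula's 80%, so not all of the gap from 80% is due to centre. Subtracting A's cost from 80.0% gives 76.9% and 73.9%.

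- *Fewer units:* 30 units cost 1.0 point (A) or 1.2 (C); 11 country groups cost 0.0 (A) or 0.6 (D).
- *No pooling:* 140 units, 78.3% to 70.9%, a cost of 7.4 points (B).
- *Sandwich SE:* 5.4 and 8.9 points at 65 and 97 units (A); 5.0 and 8.0 (B). The plan does not name the variance estimator.
- *Precision (A):* the SD of log HR rises from 0.256 to 0.275 or 0.287. That is equivalent to 65.4 × (0.256/0.275)² = 56.7 events, or 65.4 × (0.256/0.287)² = 52.0.

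**6. No loss** (about 82 events): 87.2% without centre, 84.7% at 65 units and 83.0% at 97 (A); 87.3%, 84.0% and 83.8% (D).

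**7. False non-inferiority at true HR 2** (A, full loss): 3.0% without centre, 2.6% at 65 units, 2.4% at 97 (error 0.2; nominal 2.5%). When every model in C was set to 2.5%, the cost was about 0.3 points at 30 units, 2.8 at 65 and 3.0 at 97 (error 0.6-0.7).

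**8. If sites really differ.** With an assumed site SD of 0.5 on the log hazard, the mean estimated HR at true HR 2 is 1.99 without centre, 2.00 with countries and 2.06 with 65 units. Omitting site causes almost no bias there.

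Assumptions not in the documents: gamma(1.5) site weights over 140 sites, sites spread evenly over 11 countries, 20% of patients in each minority stratum (the protocol's cap), and no true centre effect except in step 8.

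**The case against.** Four objections carry weight.

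- **The full loss is an upper allowance.** Protocol 6.6 follows every randomised patient for 7 months, protocol 6.5.2 counts withdrawal only when all four follow-up routes are refused, and SAP 10.8.1 counts events whether or not the patient is on drug. Deaths unrelated to VTE are competing events, not losses. With little loss, the reserve absorbs the cost. This stands.
- **The unit count is unknown.** The pooling rule sets a minimum size and no maximum, so coarser groups are possible and cost little. Equally, pooling is optional, and 97 is a ceiling only if it is done. Both stand.
- **Part of the cost at 97 units is a stricter test.** At equal false non-inferiority it falls to about 3 points. This stands; the cost at 65 units hardly changes.
- **Pooling is partly pre-specified.** Its criteria, minimum size and timing are given, and enrolment cannot be known earlier. This is fair, but it does not cover units without events.

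A reader might also infer that the feasibility figures contradict the sample size, since 140 × 10 = 1,400 against 1,168. The documents do not support that: the surplus can be read as recruitment reserve.

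Nor does the sparse-event argument extend to every model. Deaths are likely to be far more frequent (protocol 10.2 cites 32% and 40% six-month mortality in earlier trials), quality of life is analysed with a linear model, and neither was simulated.

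**Conclusion.** The concern holds as a loss of efficiency. At the full planned loss and with model-based SE, centre dummies cost about 2-3 points of power at 65 units and 5-6 at 97, leaving roughly 72-77% instead of 80%. A sandwich SE costs more, no pooling about 7 points, and 30 units about 1. With no loss, power is about 83-85% against 87% without centre. These sizes depend on assumed site sizes, pooling and loss, none of which the documents fix.

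A reader might infer that the primary analysis is invalid, that the hazard ratio cannot be estimated, or that false non-inferiority is inflated. The calculations do not support this: the treatment effect remains estimable despite infinite centre coefficients, and the test becomes slightly more conservative. It would also be too strong to call the trial underpowered as such, because that depends on how much follow-up is lost.

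The interaction conflict is real but narrow. The SAP already leaves the term out of both 9.9 and 10.8.1; the protocol sentence is what needs aligning.

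**What to change.** Before any treatment-level result is seen:

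1. In SAP 10.8.1, the protocol synopsis and protocol 10.6, state the primary model as Fine & Gray with treatment group and the two randomisation factors (VTE presentation, cancer status) only. Alternatively, replace centre with country or region groups listed in advance from geography and enrolment, never from observed events.
2. Carry the change into the other sparse-event Fine & Gray models: the SAP 9.11 subgroups, the individual components, symptomatic VTE and other thromboembolic events. In 9.11, omit any factor that is constant within the subgroup. With unsuspected VTE capped at 20%, that subgroup would have about 0.2 × 65 = 13 events. Changing the death, composite and quality-of-life models is optional; where a model refers back to 10.8.1, say whether it keeps centre.
3. Replace the opening sentence on centre in protocol 10.6 (center-to-center variability) and in SAP 9.9 with one common statement: no treatment-by-centre interaction enters the primary model, and centre variability is described with the forest plots. The pooling rule can then serve the plots.
4. If fine centre dummies are kept, restate power in protocol 10.1 and SAP 9.3 as about 72-77% under the full planned loss (above 80% with no loss), and state how units without events are handled.

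**Cost:** no patients or data. Site adjustment is given up or made coarser, and the change of primary model must be documented by protocol amendment or SAP revision. Country groups cost less than 1 point of power.

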#### 10.8.2 Analysis of secondary endpoints

For the secondary efficacy endpoints, analyses will be performed using the mITT analysis set.

- The individual components of the primary efficacy outcome (Proximal DVT of the lower limbs (symptomatic or unsuspected), DVT of the upper limb (symptomatic), and PE (symptomatic or unsuspected)): The same competing risk model defined in paragraph 10.8.1 for the analysis of primary efficacy variable will be employed for the analysis of the time (in days) from randomization to the first recurrent event among those included in the primary efficacy outcome recurrent (see Paragraph 9.12.1). The apixaban-to-comparator Hazard Ratio adjusted for the competing risk of death unrelated to VTE will be computed with associated two-sided 95% confidence interval. If neither the event of interest nor a competing event occurred within the 6-month follow-up, the patient will be censored at 6-month follow-up.
- Symptomatic recurrence of VTE: The same competing risk model defined in paragraph 10.8.1 for the analysis of primary efficacy variable will be employed for the analysis of the time (in days) from randomization to the first symptomatic recurrent thromboembolic event. The apixaban-to-comparator Hazard Ratio adjusted for the competing risk of death unrelated to VTE will be computed with associated two-sided 95% confidence interval. If neither the event of interest nor a competing event occurred within the 6-month follow-up, the patient will be censored at 6-month follow-up.
- Composite of primary efficacy outcome plus major bleeding: The competing risk model defined in paragraph 10.8.1 for the analysis of primary efficacy variable will be employed for the analysis of the time (in days) from randomization to the composite of primary efficacy outcome (see Paragraph 9.12.1) plus major bleeding. The apixaban-to-comparator Hazard Ratio adjusted for the competing risk of death unrelated to VTE or major bleeding will be computed with associated two-sided 95% confidence interval. If neither the event of interest nor a competing event occurred within the 6-month follow-up, the patient will be

censored at 6-month follow-up.

- Death due to any cause (OS): Overall Survival is defined as the time (in days) from randomization to the date of death for any cause. OS will be estimated according to Kaplan-Meier calculating median, first and third quartiles with the respective 95% confidence intervals. Kaplan-Meier plots with a 95% CI will be prepared. OS in the two treatment groups will be also compared by means of a Cox's proportional hazard model with treatment group, center, symptomatic vs unsuspected VTE and active cancer vs history of cancer as dummy covariates. The apixaban-to-comparator Hazard Ratio will be computed with associated two-sided 95% confidence interval. Subjects still surviving at the end of the study will be censored at the date of the last contact.
- Composite of primary efficacy outcome plus major bleeding plus death due to any cause: Event-free-survival is defined as the time (in days) from randomization to the date of event (composite of primary efficacy outcome plus major bleeding plus death due to any cause). Event free survival will be estimated according to Kaplan-Meier calculating median, first and third quartiles with the respective 95% confidence intervals. Kaplan-Meier plots with a 95% CI will be prepared. Event-free-survival in the two treatment groups will be compared by means of a Cox's proportional hazard model with treatment group, center, symptomatic vs unsuspected VTE and active cancer vs history of cancer as dummy covariates. The apixaban-to-comparator Hazard Ratio will be computed with associated two-sided 95% confidence interval. Subjects with no events at the end of the study will be censored at the date of the last contact.
- Composite of primary efficacy outcome plus death due to any cause: Event-free-survival is defined as the time (in days) from randomization to the date of event (composite of primary efficacy outcome plus death due to any cause). Event free survival will be estimated according to Kaplan-Meier and the event free survival in the two treatment groups will be compared by means of a Cox's proportional hazard model with treatment group, center, symptomatic vs unsuspected VTE and active cancer vs history of cancer as dummy covariates. The apixaban-to-comparator Hazard Ratio will be computed with associated two-sided 95% confidence interval. Subjects with no events at the end of the study will be censored at the date of the last contact.
- Any fatal or not fatal cardiovascular event: The competing risk model defined in paragraph 10.8.1 for the analysis of primary efficacy variable will be employed for the analysis of the time (in days) from randomization to the occurrence of any fatal or not fatal cardiovascular event. The apixaban-to-comparator Hazard Ratio adjusted for the competing risk of death unrelated to cardiovascular event will be computed with associated two-sided 95% confidence interval. Number and percentage of events of interest, competing events and censored patients will be presented as summary of failure outcome. Degrees of freedom (DF), Wald Chi-square and the associated p-value derived from the PHREG model will be also presented. Subjects with no events at the end of the study will be censored at the date of the last contact.
- All venous thromboembolic events (including splanchnic vein thrombosis and cerebral vein thrombosis): The same competing risk model defined in paragraph 10.8.1 for the analysis of primary efficacy variable will be employed for the analysis of the time (in days) from

randomization to thromboembolic events at sites other than DVT and PE. The apixaban-to-comparator Hazard Ratio adjusted for the competing risk of death unrelated to venous thromboembolic events will be computed with associated two-sided 95% confidence interval. Number and percentage of events of interest, competing events and censored patients will be presented as summary of failure outcome. Degrees of freedom (DF), Wald Chi-square and the associated p-value derived from the PHREG model will be also presented. Subjects with no events at the end of the study will be censored at the date of the last contact.

- Quality of life evaluation (ACTS Scale) (see Appendix 2 of the study protocol): The ACTS is a 17-item, patient-reported measure of satisfaction with anticoagulant treatment. It includes 13 items concerning the burdens of anticoagulant treatment (items 1–12 plus 1 global question about burdens) and 4 items concerning the benefits of anticoagulant treatment (items 14–16 plus 1 global question about benefits). Each of the items is scored on a 5-point Likert scale (1 = not at all; 2 = a little; 3 = moderately; 4 = quite a bit; 5 = extremely). The Burden score was calculated as the sum of questions 1 to 12 subtracted from 60, with a higher score suggesting greater satisfaction with treatment. The Benefit score was calculated as the sum of questions 14 to 16, again with a higher score suggesting greater satisfaction. The Burden subscale can take values of 12-60 and the Benefit subscale score ranges from 3 to 15. Questions 13 and 17 are excluded from the subscale calculations.

For the Burden score, no imputation on missing data will be applied if  $\geq 7$  items are incomplete; otherwise, the Burden score is calculated as the mean of the complete items score  $\times 12$ .

For the Benefit score, no imputation on missing data will be applied if  $\geq 2$  items are incomplete; otherwise, the Burden score is calculated as the mean of the complete items score  $\times 3$ .

Default summary statistics will be presented for each of the two subscales at Visit 5. For each of the subscales, a linear effects model will be estimated with treatment group, center, symptomatic vs unsuspected VTE and active cancer vs history of cancer as dummy fixed effects. The least square means for Apixaban and Dalteparin, with 95% CIs and p-value will be presented. The difference between the least squares means for Apixaban and Dalteparin will be calculated along the 95% CI and p-value.

